#### 221 **VIII.** Outcomes

- 222
- The selection of primary outcomes was based on several criteria: 1) patient-centeredness, defined 223
- as domains identified as important by children and their caregivers; as described in our previous 224
- publications; 2) availability of validated measures in English and in Spanish that could be 225
- administered in person and by phone; 3) plausibility that such measures could be responsive to an 226
- effective intervention in the target population; and 4) limited burden (e.g., time) for study 227
- participants. On this basis, we selected two NIH Patient-Reported Outcomes Measurement 228
- Information System (PROMIS) measures as primary outcomes (1 for the child and 1 for the 229
- caregiver). Several measures were selected for secondary outcomes to address recommendations of 230
- 231 national asthma guidelines, expressed preferences of caregivers and other stakeholders, and to
- compare results of the CHICAGO Plan with previous studies. 232
- 233
- A. Primary outcomes 234

1. The change in asthma impact at 6 months compared to the baseline assessed in the ED served as 235 the primary outcome in children. In children 5 to 7 years, we assessed asthma impact using the

- 236 PROMIS Parent Proxy Short Form v1.0 – Asthma Impact 8a. In children 8 to 11 years, we used
- 237
- the PROMIS Pediatric Short Form v1.0 Asthma Impact 8a. 238
- 239
- 2. The change in Satisfaction with Participation in Social Roles at 6 months compared to the 240
- baseline assessed in the ED served as the primary outcome in the caregiver. We used the PROMIS 241 Short Form v1.0 – Satisfaction with Participation in Social Roles 4a. 242
- 243
- 244 B. Secondary outcomes
- For children: 245
- 246 1) The Childhood Asthma Control Test (cACT) at 6 months compared to the baseline assessed in the ED 247
- 2) Acute care visits at 6 months (number of all-cause urgent care visits, ED visits, 248
- hospitalizations, using electronic health records) 249
- For caregivers: 251
- 252 1) Pediatric Asthma Caregiver's Quality of Life Questionnaire (PACQLQ) at 6 months compared to the baseline assessed in the ED 253
- 2) NIH PROMIS measures for anxiety, depression, fatigue, sleep disturbance at 6 months 254 compared to the baseline assessed in the ED 255
- 256 257

- 258 Indicators of guideline-consistent asthma care provided on ED discharge:
- 1) Systemic corticosteroids prescribed for use at home (yes/no)

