#### 270 IX. Analysis plan

271

269

- All primary and secondary outcomes were analyzed according to the intention-to-treat principle.
- All randomized subjects were included in the primary analysis, unless subjects were terminated
- due to ineligibility. Baseline sociodemographic and clinical characteristics in the intervention and
- control groups were compared using the frequency and percentages for categorical variables and
- 276 median with inter-quartile or mean with standard error for continuous variables. For bivariate
- analyses, the pairwise comparisons between three intervention arms for the change in primary and
  some secondary outcomes from baseline to 3 or 6 months were tested by Wilcoxon rank sum test.
- The W statistic, p-value and mean rank were reported together with horizontal mirror bar plots. For
- primary outcomes, a statistical significance occurred when p-value was less than 0.0167 after
- Bonferroni correction for three pairwise comparisons (0.05/3). In addition, chi-square tests were
- also conducted for other secondary outcomes.
- 283
- To address missing data in the analyses, we checked the missing completely at random (MCAR) assumption and then employed a multiple imputation strategy. Using a logistic regression method described in Hedeker & Gibbons (2006), we found that the current outcome missingness was not statistically associated with previous observed outcomes across time. Additional characteristics comparisons between participants with and without missing primary outcomes across time was also done using Chi-square tests for categorical variables and Mann-Whitney U test for continuous
- variables. No statistical difference was observed between the two groups (i.e. with and without
- 290 variables. No statistical difference was observed between the two groups (i.e. with and without 291 missing primary outcomes). We therefore used a fully conditional specification (FCS) approach to
- impute the missing values with variables of interest in the primary analysis models for 30
- 293 imputations. The raw and imputed data had similar distributions (mean, standard deviation,
- 294 minimum and maximum values).

- 296 Since the two primary outcomes were not normally distributed and our data satisfied the MCAR
- assumption, we used generalized estimating equations (GEE) to examine the effect of intervention
- group on outcomes at 3 and at 6 months compared to that of the enhanced usual care group using

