- ordinal logistic regression models; the continuous dependent variables were categorized into
- quartiles. The main predictors of the unadjusted GEE models were time (0, 1, 3, and 6 months),
- intervention group, and their interactions. In an adjusted model, we added pre-specified covariates
- 302 including, race (Black vs. non-Black), ethnicity (Latino vs. non-Latino), gender (boy vs. girl),

health insurance (Public aid vs. Other), site enrolled (sites 1 to 6), number of all-cause acute care

use in the 12 months prior to enrollment (at least one vs. none). To access the intervention effect

between groups across time, we reported our results as odds ratios (ORs for higher quartiles) of

- interactions between study group and time and their 98% confident intervals [CIs; corresponding
   to a 2-sided alpha=0.0167) to account for Bonferroni adjustments for the three pairwise
- 307 to a 2-sided alpha=0.0167) to account for Bonferroni adjustments for the three pairwise 308 comparisons.
- 309

310 In secondary analyses, we explored heterogeneity of treatment effects by adding a three-way

interaction between intervention, time, and a subgroup factor in the model described previously.

312 Pre-specified subgroup factors included race (Black vs. non-black), ethnicity (Latino vs. non-

Latino), gender (boy vs. girl), and number of all-cause acute care use in the 12 months prior to enrollment (at least one vs. none).

315

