316 Power / sample size calculation. The power analyses did not incorporate adjustment for the presence of two primary outcomes. Such an adjustment is not commonly made in biomedical 317 trials, as multivariate (viz. MANOVA) analyses are not commonly conducted. The power analysis 318 for single outcomes employed the Rochon (1991) method based on Hotelling's T-squared, which 319 was adapted to a 3-group comparison by adjusting the alpha level using a Bonferroni-style 320 technique. This approach tends toward a conservative (larger) sample size. We proposed to 321 enroll and randomize 640 participants over 18 months (~200-215 for each of the 3 treatment 322 groups). Assuming evaluable data in 80% of enrolled participants (n=512) at 6 months (the time-323 point for the analyses of the primary outcomes), sample size calculations suggest ample power. 324 Our approach was based on the methods of Rochon, with a Bonferroni adjustment for 3 pair-wise 325 comparisons (2-sided  $\alpha = 0.05/3 = 0.0167$ ; enhanced usual care and two active intervention groups), 326 power 80%, 4 measurements per individual (0, 1, 3, and 6 months), within individual correlation 327 0.80, correction for within ED clustering (design effect of 2), and a coefficient of determination 328 (R2) for control of individual-level demographics = 0.15. Based on these considerations, a sample 329 size of 426 (well within the expected sample size of 512) was estimated to be sufficient for a 330 minimum detectable difference of 0.35 standard deviations (SDs) (midway between Cohen's 331 "small" (0.2 SDs) and "medium" (0.5 SDs) effect sizes) for each of the two primary continuous 332 outcomes compared pairwise across the three treatment groups. The minimum detectable 333 difference of 0.35 SDs corresponds to sufficient power to detect a T-score difference of 3.5, which 334 is approximately mid-way between estimates of the minimum important difference (MID) for 335 PROMIS T-scores (2 to 5). 336

- 337
- 338

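### Does the 0.0167 threshold need a further correction because there are two primary outcomes?

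*Combined protocol and SAP*

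**What the plan says.** Section VIII selects two NIH "Information System (PROMIS) measures as primary outcomes (1 for the child and 1 for the" caregiver). Change in asthma impact at 6 months is "the primary outcome in children". Change in satisfaction with social roles from the "baseline assessed in the ED served as the primary outcome in the caregiver".

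Section IX sets the threshold: for "primary outcomes, a statistical significance occurred when p-value was less than 0.0167 after" a correction, whose basis it gives as "Bonferroni correction for three pairwise comparisons (0.05/3"). The confidence intervals for the GEE odds ratios use the same alpha, "to account for Bonferroni adjustments for the three pairwise" comparisons. The GEE is described as examining the effect of intervention "group on outcomes at 3 and at 6 months compared to that of the enhanced usual care group using" ordinal logistic models, so the contrasts with enhanced usual care are the ones named there.

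The sample-size paragraph of Section IX addresses the second outcome directly: "The power analyses did not incorporate adjustment for the" fact that there are two primary outcomes. It says such adjustment is uncommon because multivariate analyses are uncommon. It then sizes the trial for a single outcome: 426 participants for 0.35 SD at two-sided 0.0167 and 80% power, against 512 expected to be evaluable (80% of 640).

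**The concern.** Three pairs of arms on two outcomes make six primary comparisons at 6 months, and the divisor in 0.05/3 counts only the pairs. The plan does not say whether a win on either outcome is enough, whether both must be won, or whether child and caregiver are separate families at 5% each. Section III states the primary aim as a single comparison of effectiveness across three strategies. If one outcome crossed 0.0167, the other did not, and the strategy were then called effective overall, the chance of a false claim would exceed 5%. The reason offered in the sample-size paragraph, that multivariate analysis is uncommon, does not bear on type I error: Bonferroni or Holm across outcomes needs no multivariate model.

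**Working it through.** **Inputs from the plan.** Three arms of about equal size; three pairwise tests; two-sided alpha 0.05/3; two primary outcomes; N = 426 for 80% power at 0.35 SD; 512 expected evaluable. The correlation between the two outcomes is not given, so it is varied from r = 0 to 0.9. The 0.80 in the sample-size paragraph is a within-person correlation over repeated measurements and cannot stand in for it.

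**The plan's figure.** 0.05/3 = 0.016667, which rounds to 0.0167. It reproduces.

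**Error within one outcome.** The two-sided critical value is z = 2.394. With three equal arms, at least one pair is significant when the range of three independent standard normals exceeds 2.394 × √2 = 3.386. The studentized range distribution gives a probability of 0.0440, so each outcome is controlled at about 4.4%.

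**Error if either outcome may win.** For independent outcomes, 1 − (1 − 0.0440)² = 0.086. For correlated outcomes a simulation is needed (normal arm means, three equal arms, one million trials per null case). The entries are the chance of at least one false significant result at 0.0167. Cases with a true effect use 0.35 SD and N = 512.

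| Situation | r = 0 | r = 0.5 | r = 0.8 | r = 0.9 |
|---|---|---|---|---|
| Global null, all three pairs | 8.6% | 8.1% | 7.0% | 6.3% |
| Global null, enhanced-usual-care pairs only | 6.2% | 5.8% | 5.1% | 4.5% |
| One arm differs on one outcome | 6.0% | 5.8% | 5.3% | 5.0% |
| One arm differs on both outcomes | 3.3% | 3.1% | 2.7% | 2.5% |

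The last digit can move by 0.1 between runs.

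**Error if both must win.** Under the global null it is 0.2% at r = 0, 1.8% at r = 0.8 and 2.5% at r = 0.9. It cannot exceed the 4.4% of a single outcome.

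**Cost of splitting alpha over six tests.** 0.05/6 = 0.0083, with critical value 2.638. Take the plan's own calculation as the anchor: the standardized signal at N = 426 is 2.394 + 0.842 = 3.236.

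- N needed at 0.0083: 426 × ((2.638 + 0.842)/3.236)² ≈ 493.
- Signal at 512: 3.236 × √(512/426) = 3.547.
- Power at 0.0167: Φ(3.547 − 2.394) = 0.876.
- Power at 0.0083: Φ(3.547 − 2.638) = 0.818.
- Holm over six tests at 512, by simulation: about 0.83 if one outcome is affected and 0.856 to 0.864 if both are.

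These power figures scale a continuous-outcome calculation and are only approximate for the quartile GEE. Simple sample-size formulas with the listed inputs do not return 426, so it serves only as an anchor.

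**The case for a change.** The strongest case for a change is that a disclosure about power is not a decision rule. A mixed result, with one outcome significant and the other not, is quite possible, and the plan does not say what may then be concluded about a strategy. The remedy looks cheap: six adjusted p-values and no new data. Even plain 0.05/6 needs about 493 evaluable participants, below the 512 expected.

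Part of this stands. No sentence states how the outcomes combine, and the remark about multivariate analysis is a weak reason.

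The rest does not carry. The scope of 0.0167 is given each time it appears, so a reader is not led to think that it covers both outcomes. The inflation needs an either-wins rule, and Section III speaks only of comparing effectiveness. Even under that rule the excess depends on conditions: it largely disappears for the enhanced-usual-care contrasts when the outcomes are highly correlated, and it is absent when one arm affects both outcomes. The margin over 493 is also thin, since Sections IV, VII and XI report low randomization, difficult retention and slow enrollment. Finally, the document is dated 12-01-2017 and data collection ended on March 31, 2017. A rule added at that point would be post hoc and could not restore prespecification.

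**Conclusion.** No change follows. The plan measures a different construct in each of two people, calls each the primary outcome for that person, powers each alone and corrects each for three arm comparisons. The natural reading is two families, each held at about 4.4%, with no 5% claim across the pair; if both outcomes had to succeed, error would be lower still. An analyst reporting child and caregiver results side by side at 0.0167 does what the text supports. The gap is a missing sentence that a sensible report supplies.

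Correcting across all six tests is a trade-off on which statisticians differ. It would guard against an error of roughly 4.5% to 8.6% under a global null and an unstated either-wins rule. It would cost about 1 to 6 points of power at 512 evaluable: 87.6% against 86.4% at best with Holm and 81.8% with plain 0.05/6.

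The 4.4% assumes equal arms and normal-theory tests. The either-wins figures rest on an assumed between-outcome correlation of 0 to 0.9. The conclusion would alter only if a report used one significant outcome to claim overall effectiveness with 5% error across both.

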2. ED-plus-home. Participants randomly allocated to the ED-plus-home intervention received 145 the same ED-only intervention described above but were also offered up to five home visits 146 over 6 months conducted by a CHW visits to: 1) assist in the implementation of the ED 147 discharge instructions, 2) update the asthma treatment plan with input from the patient's 148 ambulatory clinician utilizing the CAPE tool called the Asthma Home Plan (APPENDIX 149 A2), 3) develop a plan to manage asthma during school hours (e.g., access to quick-relief 150 medications, action plan in case of respiratory difficulty), and 4) develop a specific and 151 feasible plan to reduce environmental triggers at home (e.g., environmental tobacco smoke, 152 roach, mice). Home visits were scheduled for 60 to 90 minutes, and occurred 153

approximately at 2-3 days, 2 weeks (14 days), 1 month (30 days), 3 month (90 days), and 6 154 months (180 days) after ED discharge. 155

- 3. Enhanced usual care. Based on stakeholder feedback, we modified usual care so that 157 children in the "usual care" group also received teaching about appropriate MDI technique 158 using teach-to-goal methodology and two MDI spacers free-of-charge, as well as doorknob 159 hangers depicting facts about asthma unrelated to the study interventions. We therefore 160 refer to this group as "Enhanced usual care." To describe usual care at each site, the site 161 project manager conducted chart abstractions (masked to treatment assignment). Site 162 project managers were to complete chart abstractions within 3 business days of enrolling 163 the participant in the study. 164
- 165

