#### 166 VI. Randomization

167

168 Randomization occurred at the patient level, with permuted block sizes stratified by site and race

169 (black vs. non-black). Based on data from the Clinical Centers, we expected about 70% of enrolled

170 participants to be black, 23% to be white, and that the remainder would be mostly Asian. Of the

- 171 planned enrollment of 640 children, we expected 15% to be Hispanic/Latino. Stratification by race
- for the purposes of randomization was "Black" (those who selected Black or African American,
- includes multi-race if at least one race was Black or African American) vs. "non-Black" (American
   Indian/Alaskan Native, Asian, Native Hawaiian or other Pacific Islander, white, and multi-race if
- Indian/Alaskan Native, Asian, Native Hawaiian or other Pacific Islander, white, and mulnone are Black or African American).
- 176

The CHICAGO Plan Research Electronic Data Capture (REDCap) system for study personnel
 (available 24 hours x7 days/week) provided the random treatment assignment: ED-only, ED-plus-

- 179 home, or Enhanced usual care.
- 180

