- 260 2) Inhaled corticosteroids or another controller medication prescribed for use at home (yes/no)
- 261 3) Quick-relief medications prescribed for use at home (yes/no)
- 262 4) Follow-up appointment scheduled (yes/no)
- 263 Child's/caregiver's self-management practices after ED discharge:
- 1) Filled prescriptions for systemic corticosteroids within 7 days of ED discharge (yes/no)
- 265 2) Filled prescription for inhaled corticosteroids or other asthma controller within 7 days of
   266 ED discharge (yes/no)
- Attendance at outpatient appointment with patient-identified asthma provider within 4
   weeks of ED discharge (yes/no)

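### The yes/no secondary outcomes get only an unstratified chi-square test although randomization was stratified by site and race, so power may be lost if practice differs between EDs

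*Combined protocol and SAP*

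**What the plan says.** Section VI: "Randomization occurred at the patient level, with permuted block sizes stratified by site and race". With six sites and two race groups this makes 12 strata. Block sizes are not given.

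Section IX describes two kinds of simple test. Changes in the primary outcomes and in "some secondary outcomes from baseline to 3 or 6 months were tested by Wilcoxon rank sum test". Then "In addition, chi-square tests were" carried out for the other secondary outcomes. Neither test is described as stratified. Section IX does not list which outcomes get the chi-square. I take them to include the seven yes/no items in Section VIII: four on care at ED discharge (for example "Quick-relief medications prescribed for use at home (yes/no") and three on self-management afterwards.

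For the two primary outcomes Section IX adds a GEE ordinal model. The covariates of its adjusted version are given as "including, race (Black vs. non-Black), ethnicity (Latino vs. non-Latino), gender (boy vs. girl" and, further on, "site enrolled (sites 1 to 6), number of all-cause acute care". Both randomization factors are therefore in that model. No such model is described for the yes/no outcomes.

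The significance rule covers only the primary outcomes: "primary outcomes, a statistical significance occurred when p-value was less than 0.0167 after" Bonferroni correction. No level is stated for secondary outcomes.

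**The concern.** When arms are balanced within each site, a difference in prescribing between two EDs cannot make one arm look better than another. An unstratified test does not know this. It estimates its error from all variation between children, including variation between sites, so its standard error is too large and its p-values lean high.

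The four ED-discharge indicators are where this is most likely to matter. Prescriptions and follow-up appointments are arranged at the EDs, and the chi-square is the only test the plan offers for them. They also help to interpret the trial. Section X notes that, without improvement in outcomes, failed implementation and lack of efficacy are hard to tell apart. Appendix B uses ED chart reviews to look for contamination between arms. A real change in ED care that the test misses could be misread as failed delivery or as contamination.

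**Working it through.** **Plan figures checked.** The Bonferroni level reproduces: 0.05/3 = 0.0167. The Appendix B monthly targets sum to 1.7 + 17.5 + 3.9 + 4.0 + 12.7 + 2.6 = 42.4, and 42.4 × 15 months = 636, against the planned 640. The plan gives no power figure for the yes/no outcomes, so there is none to reproduce.

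**Inputs.** Site shares w are 4%, 41%, 9%, 9%, 30% and 6% (Appendix B targets divided by 42.4). Assumed, because the documents are silent: the site rates p, a two-sided 5% level, pairwise comparison of arms, and no outcome difference by race.

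**Formula.** Let r be the share of outcome variance that lies within sites:

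r = Σ w p(1−p) / [p̄(1−p̄)], with p̄ = Σ w p.

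With allocation balanced within sites, the actual error of the unstratified test is 2 × [1 − Φ(1.96/√r)].

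The extra sample that offsets the inflated variance is 1/r − 1. This is exact at 50% power. At 80% power it is [(1.96/√r + 0.84)/(1.96 + 0.84)]² − 1.

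**Result.** Six evenly spaced rates were assigned to the six sites in all 720 possible orders. Medians:

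| Site rates | r | 1.96/√r | Actual error | 1/r − 1 | Extra at 80% power |
|---|---|---|---|---|---|
| 40-60% | 0.985 | 1.975 | 4.8% | 2% | 1% |
| 30-70% | 0.938 | 2.024 | 4.3% | 7% | 5% |
| 20-80% | 0.858 | 2.116 | 3.4% | 17% | 11% |

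The order matters. The smallest r for 20-80% is 0.721, with the two largest sites at opposite ends. Then 1.96/√0.721 = 2.308 and the error is 2.1%. The smallest r for the narrower ranges is 0.969 and 0.876, with errors of 4.7% and 3.6%.

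**Simulation.** This used 12 strata, Appendix B site sizes, about 213 children per arm, assumed blocks of 6, one pair of arms and 20,000 runs. The Monte Carlo standard error at 5% is √(0.05 × 0.95/20,000) = 0.0015. Each cell gives chi-square, then Cochran-Mantel-Haenszel (CMH).

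| Assumed site rates | Error | Power for +10 points |
|---|---|---|
| No difference | 0.052 / 0.052 | 58% / 58% |
| 50-70% | 0.050 / 0.052 | 59% / 59% |
| 40-80% | 0.038 / 0.046 | 60% / 64% |
| Two largest sites 30% and 80% | 0.032 / 0.052 | 55% / 63% |
| 20-90% | 0.027 / 0.050 | 57% / 68% |

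The stratified test costs essentially nothing when sites are alike.

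**Wilcoxon tests of the primary outcomes.** The power section assumes a design effect of 2 for clustering within EDs. From 1 + (m − 1) × ICC = 2:

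- m = 640/6 = 106.7 gives ICC 1/105.7 = 0.0095.
- m = 512/6 = 85.3 gives 0.012.
- A size-weighted m of 181 gives 0.006.

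With r = 1 − 0.0095, the level moves from 0.0167 to 0.0162. Simulated power for 0.35 SD was 76% for both the Wilcoxon and the van Elteren test.

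**The case against.** The strongest reply is that nothing in the documents shows that practice differs between EDs. The chart abstraction is there "To describe usual care at each site"; that is a plan to describe practice, not evidence of variation. Care was given by individual clinicians. This stands: the direction of the effect is certain, its size is not. A reader might infer that these tests definitely run below their nominal level, or that the loss equals some 40% more children. The documents support neither. The first needs material site differences. The second needs the two largest sites near opposite ends of a very wide range, a more extreme layout than any of the 720 even-spread orders.

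A reader might also extend the point to the Wilcoxon tests. For the primary outcomes that fails on the plan's own clustering figure. Those tests are presented as bivariate analyses, and the adjusted model for the same outcomes already contains site and race. The implied ICC of about 1% was set for the primary outcomes, however, so it does not bound clustering in prescribing.

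Three more replies have weight. Filling prescriptions and attending appointments are family behaviours, so the argument from ED practice is weaker there. The calculation is idealized: block sizes are unknown, some strata are very small, and Section IV reports slow randomization. The document is dated December 2017, after data collection was due to end in March 2017, and reports the tests as done, so a new test is a post hoc change. These limit emphasis. They do not give the yes/no outcomes an analysis that uses the randomization strata.

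**Conclusion.** The point holds for the yes/no secondary outcomes, chiefly the four ED-discharge indicators. Their only described test ignores the strata used in randomization. The error is one-sided: the chi-square remains valid and false positives are not inflated, but a real effect may be missed.

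The size runs from nil, if sites do not differ, through a typical 4.8% to 3.4% actual error at nominal 5% for the ranges tabulated, to about 2% in an unfavourable 20-80% layout. It rests on assumed site rates, Appendix B accrual shares, allocation balanced within sites, no race effect and an assumed 5% level. The primary-outcome conclusions are not affected.

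**What to change.** For each yes/no outcome, use a CMH test with a stratified risk difference and its confidence interval, or a logistic model with site and race as covariates. Stratify by site and race, and state a rule for pooling sparse cells, since two sites expect only 1.7 and 2.6 children a month.

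Because the tests are reported as already run, label this as a change made after data collection and show the unstratified chi-square alongside. State the significance level that applies to secondary outcomes. Report the indicator rates by site, so that readers can see whether the change matters.

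A van Elteren test beside the primary-outcome Wilcoxon tests is optional, as a sensitivity analysis only.

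The cost is a different procedure call and a few table columns. Site and race are already held as randomization factors, so no new data are needed.

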- E. 12-month follow-up contact after discharge (in person or by telephone; ~40 minutes). We 215
- proposed re-assessing outcomes at 12 months to examine the durability of effects observed at 6 216
- months. Despite significant efforts, retention in the study also proved to be challenging, and 217

#### therefore the 12-month follow-up visit was discontinued at the request of PCORI in September 218

2016. 219

#### 220

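### On its plain reading, the imputation model lacks the arm-by-subgroup term, so heterogeneity estimates taken from imputed data shrink toward no difference

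*Combined protocol and SAP*

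**What the plan says.** The relevant text is in section IX (Analysis plan) of the combined protocol and SAP, except where noted.

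- **Scope of imputation.** "To address missing data in the analyses, we checked the missing completely at random (MCAR) assumption and then employed a multiple imputation strategy". Nothing limits this to the primary analysis.
- **Content of the imputation model.** Fully conditional specification (FCS) was used to "impute the missing values with variables of interest in the primary analysis models for 30" imputations. This is the only description given. It names a set of variables. It does not list terms, mention interactions, or say whether imputation was run separately by arm.
- **Primary models.** The predictors are time (0, 1, 3 and 6 months), "intervention group, and their interactions. In an adjusted model, we added pre-specified covariates". Those covariates are race, ethnicity, gender, insurance, site and acute care use in the prior 12 months. None is interacted with arm.
- **Heterogeneity.** The secondary analysis adds a three-way "interaction between intervention, time, and a subgroup factor in the model described previously". The pre-specified factors are race, ethnicity, gender and prior acute care use. All four are already main effects in the adjusted primary model.
- **Missingness.** The power paragraph plans for one level: "Assuming evaluable data in 80% of enrolled participants (n=512) at 6 months". Section VII.E reports on conduct: "Despite significant efforts, retention in the study also proved to be challenging". No actual rate is given.

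**The concern.** An imputation model should contain every association that the later analysis will estimate. If it leaves out the arm-by-subgroup term, the imputed values are drawn as though the treatment effect were the same in every subgroup, except for what they inherit from a child's own earlier visits. Mixing them with observed values dilutes any real interaction, always toward no difference.

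Examining heterogeneity is the first secondary aim in section III, and race and ethnicity are two of the four factors in a trial motivated by disparities. The plan's reported check, that raw and imputed data had similar means, standard deviations and ranges, would not show the problem: marginal distributions can agree while an interaction is lost.

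The plan also states that the data satisfied missing completely at random (MCAR). Under that assumption GEE on the observed data recovers the interaction without imputation. On the plan's own terms, it is the imputation that would introduce the bias.

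**Working it through.** **The plan's own figures.** The documents give no number for the imputation or the heterogeneity analysis, so there is none to reproduce on this point. The planned missing share follows from the power paragraph: (640 − 512)/640 = 20%. That paragraph also supplies the visit schedule and the within-person correlation of 0.80 used below. Its sample size of 426 can be reproduced from the stated inputs if the difference is assumed to grow linearly to 0.35 SD at month 6. The Hotelling calculation gives 82.9 per arm, rounded up to 83; 83 × 0.85 × 2 = 141.1, rounded up to 142; 142 × 3 = 426. The time profile is an assumption.

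**Hand calculation.** Let m be the share missing at month 6, and g the fraction of the true month-6 interaction that an imputed value inherits from earlier visits. Then

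share kept = (1 − m) + m × g.

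- *No follow-up observed.* Only baseline predicts, and randomization makes the baseline interaction zero, so g = 0. Share kept = 1 − m: 0.80 at 20% missing, 0.60 at 40%.
- *Only month 6 missing.* With three earlier visits at equal correlation 0.80, the slope on each is 0.80/(1 + 2 × 0.80) = 0.308.
  - Interaction constant from month 1: g = 0.308 × (0 + 1 + 1) = 0.615. Share kept = 0.80 + 0.20 × 0.615 = 0.92 at 20%, and 0.60 + 0.40 × 0.615 = 0.85 at 40%.
  - Interaction growing linearly: g = 0.308 × (0 + 1/6 + 1/2) = 0.205. Share kept = 0.80 + 0.20 × 0.205 = 0.84 at 20%, and 0.60 + 0.40 × 0.205 = 0.68 at 40%.

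**Simulation.** Settings: 6,000 children per dataset (large, to isolate bias), 60 datasets, 3 imputations, continuous outcome, correlation 0.80, a 70/30 subgroup split (section VI expects about 70% Black) and MCAR dropout. FCS used arm, the subgroup main effect and earlier outcomes. Monte Carlo error is about 0.01. Share of the true 6-month interaction kept:

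| Missing at month 6 | Interaction over time | Only month 6 missing | Staggered dropout | All follow-up missing |
|---|---|---|---|---|
| 20% (planned) | constant | 0.92 | 0.87 | 0.79 |
| 20% (planned) | linear | 0.85 | 0.83 | 0.77 |
| 30% (assumed) | constant | 0.90 | 0.80 | 0.70 |
| 30% (assumed) | linear | 0.78 | 0.73 | 0.70 |
| 40% (assumed) | constant | 0.86 | 0.74 | 0.61 |
| 40% (assumed) | linear | 0.70 | 0.64 | 0.61 |

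These agree with the hand calculation to within about 0.03. A repeat simulation of the same structure gave 79–93% at 20% missing and 58–86% at 40%. Taken together, the ranges are 77–93% and 58–86%.

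**Comparison.** With arm-by-subgroup terms in the imputation model, recovery was 97–102% in every scenario (96–103% in the repeat). Observed data alone did equally well under MCAR.

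**In score units.** Suppose the true interaction were 3.5 T-score points, the difference the trial was sized to detect between arms. The expected estimate would be 0.77 × 3.5 = 2.7 to 0.93 × 3.5 = 3.3 points at 20% missing, and 0.58 × 3.5 = 2.0 to 0.86 × 3.5 = 3.0 points at 40%.

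**The case against.** The strongest reply is that the omission is inferred. The plan names variables and is silent on functional form. Interactions may have been included, imputation may have been run by arm, and the heterogeneity models may have used observed data. This stands, which is why the conclusion is conditional. But the primary models are the only reference given, they hold the subgroup factors as main effects only, and imputation is introduced for the analyses in general. An analyst following the text as written would leave the term out.

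Second, a reader might infer that imputed outcomes carry no interaction at all, so that the loss equals the missing fraction. That holds only for children with no observed follow-up. Where month 1 or 3 is observed and used as a predictor, the loss at 20% missing can be as small as 7–8%.

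Third, heterogeneity is a secondary analysis that the plan itself calls exploratory. That limits the weight of the point without removing it, since the estimate still bears on a stated aim.

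Finally, a reader might object that the imputation rule also leaves out the childhood Asthma Control Test, the caregiver quality-of-life score, the other PROMIS scores and health-record visit counts. The 6-month questionnaires will tend to be missing together with the primary outcome, no gain has been calculated, and under MCAR such predictors are not needed for validity. Adding them is optional.

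**Conclusion.** The point holds conditionally. On the plain reading of section IX, the heterogeneity models ask for a term that the imputation model does not contain. If they were fitted to the imputed data, a true 6-month arm-by-subgroup effect is shrunk to about 77–93% of its size at the planned 20% missing, and to about 58–86% if 40% were missing.

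These figures rest on a linear scale, correlation 0.80 at all visits, MCAR, and interaction profiles that are either constant or linear over time. The plan fits ordinal logistic GEE to quartiles, so the direction carries over but the size is approximate. Only 20% is documented; 30% and 40% are assumptions, and the remark on retention gives no rate.

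Two stronger readings are not supported. The omission does not bias the primary arm comparison, because arm and arm-by-time are in the named models. Nor can one say that an absence of heterogeneity was manufactured: the documents report no heterogeneity result and do not say which data those models used.

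**What to change.** 1. List the imputation terms, and state whether the heterogeneity models use imputed or observed data.
2. For the heterogeneity analyses, impute with the four visits in wide form and include arm-by-subgroup terms for each factor at each visit. Imputing within arm, with the subgroup factors as predictors, is an alternative.
3. If imputing within arm, pool small sites in that step. The smallest target in Appendix B, item (1), is 1.7 per month over 15 months: 1.7 × 15 = 25.5 children, or 25.5/3 = 8.5 per arm, too few for stable site terms.
4. Report the observed-data heterogeneity estimate beside the imputed one. Under MCAR the two should agree; a material gap would call for explanation.
5. Baseline scores and health-record acute-care counts may be added as auxiliary predictors, but this fix does not depend on them.

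The cost is a rerun of the imputation on data already collected, slightly less precise subgroup estimates, and the pooling of small sites if the within-arm route is taken. The primary analysis need not be re-imputed on this account.
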